2 BACKGROUND INFORMATION AND SCIENTIFIC RATIONALE

2.1 Background Information

Despite strong evidence that preemptive therapy is highly effective in preventing cytomegalovirus (CMV) end organ disease after HCT, CMV monitoring adherence decreases significantly after day 100, when patients typically leave the care of the transplant team. Preliminary data (section 2.1.4.) indicate that fewer than 50% of patients who are recommended to continue CMV testing do so throughout the recommended testing period; the drop-off starts as soon as two months after discharge. Consequently, the incidence of late CMV end organ disease (defined as disease occurring after day 100 after HCT) remains high at 8% in the current era with recommended surveillance testing and preemptive therapy. Half these cases are CMV pneumonia, which continues to carry a substantial risk of death (section 2.1.3). In a recent multicenter randomized trial of prophylaxis compared to preemptive therapy for the prevention of late CMV disease the incidence of late CMV disease was only 2%¹. During the trial, study coordinators were in close contact with study subjects, resulting in a CMV monitoring completion rate of 93%. Similarly, high rates of adherence are also routinely achieved during the first 3 months after HCT while patients are treated in specialized cancer centers, and these adherence rates correlate with CMV disease rates between 0 and 3%. However, outside of the clinical trial setting, the requirement for weekly blood draws is burdensome for patients late after HCT. In general, the frequency of CMV monitoring decreases as the frequency of doctor's office visits decreases, resulting in missed opportunities for preemptive therapy. Finger-stick collected DBS CMV testing would allow subjects to collect their samples at home and mail the cards directly to the laboratory. This method of CMV PCR testing has been validated in transplant recipients and has sufficient sensitivity to detect viral loads appropriate for a preemptive therapy approach late after transplantation 2,3 .

In addition, mobile technology can be used to automate simple reminder and notification systems and to facilitate ongoing communication among the patient, their primary oncologist, and the transplant center. There is good evidence ^{4,5} that these types of reminders are efficacious for improving medication adherence; however, it has not yet been tested in the setting of post-transplant virologic monitoring.

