2.1.2 Importance and Risk Factors for Late CMV Disease after HCT

The phenomenon of late CMV disease was first recognized in the early 1990s when the first reports were published about effective prevention of early CMV disease, and, at the same time, cases of delayed onset CMV disease were observed ¹³. Since then, a substantial body of literature indicates that CMV disease can be prevented during the first 3 months after HCT when antiviral agents are given prophylactically at engraftment or pre-emptively for pp65 antigenemia or detection of CMV DNA by PCR, with improved survival in selected high-risk patients ^{14,15}. However, once prophylaxis is stopped or the preemptive strategy is applied less rigorously, CMV disease incidence rises again. As a result, the majority of CMV disease now occurs after day 100, resulting in a much longer period of high risk ^{2,3,14,16-19}. Late CMV disease (defined as disease presenting after day 100 after HCT) occurs primarily between day 100 and day 365 after transplant. Both late CMV infection and disease remain independent predictors for mortality after HCT, even though patients at highest risk for late CMV infection and disease can be identified by day 100². Without intervention, the incidence of late CMV disease ranges from about 10% to 17% of CMV seropositive recipients who are alive at day 100². Mechanistically, lymphopenia and delayed reconstitution of CMV-specific T-cell responses are the immunologic defects that predispose patients to late CMV disease seems to occur almost exclusively in patients who had evidence of primary CMV infection during the first 100 days and the incidence of late CMV disease is similar to that observed in CMV seropositive recipients ³.

Approximately 50% of patients with late CMV disease present with pneumonia, followed by gastrointestinal disease (40%) and other manifestations such as retinitis, encephalitis, and late graft failure ³.

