11.1.2 Secondary Endpoint

As a secondary endpoint we will be comparing the incidence of late CMV disease by one year post HCT between the two randomized groups using competing risk regression with death treated as a competing risk event ⁴². Using similar methods, we will also compare the CMV disease incidence of trial participants compared to subjects who received HCTs at the clinical sites in the similar time period but did not participate in the trial. As expected, the planned trial would not be sufficiently powered to detect a difference in late CMV disease incidence from 8% (current standard care) to 2% (observed in clinical trial). A trial powered for that detectable effect size would require 330 subjects to have 80% power (one-sided p values 0.05).

To determine the rate of CMV disease at participating sites during the clinical trial we will collect concurrent retrospective baseline data as well as CMV disease and survival data from subjects that were eligible for randomization but decided not to participate (the majority of subjects return to the transplant center at one year). The purpose of this analysis is to determine whether the subjects who participated in the trial are representative of the population at risk for late CMV disease and whether the phenomenon of late CMV disease continues to occur throughout the study period.

To assess the correlation of CMV viral load between DBS and plasma samples, we will use linear model. Other outcomes will be tabulated and compared between groups using Chi-Square, Fisher's exact, and log rank tests, as appropriate.

The relative contribution of mobile phone reminders, subject adherence to the device, and failures of the testing kit itself will be analyzed among subjects randomized to the DBS arm who did not reach the 90% adherence threshold.

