3.1.3. Exploratory Objectives

- 1. Evaluate the transit time from self-collection to arrival in the laboratory
- 2. Assess the mechanism for non-compliance as defined by a missing DBS sample PCR result (e.g. mobile technology failure, sample collection failure, sample delivery failure, sample viability failure)
- 3. Compare the performance characteristics of concurrently drawn DBS with plasma CMV PCR (e.g., sensitivity and specificity concordance)
- 4. Determine if the randomized study population is representative of the population as a whole
- 5. Obtain a population-based estimate of late CMV disease in observational and randomized cohorts
- 6. Describe local provider CMV treatment algorithms
- 7. Assess participant and provider satisfaction of DBS testing

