3.2.2. Secondary Outcome Measures

- 1. The total number of recommended CMV monitoring tests that were completed per participant by 1 year after HCT
- 2. Number of participants in DBS and standard of care arms with end-organ CMV disease, possible and proven/probable by 1 year after HCT; CMV syndrome will not be used to define CMV disease
- 3. Number of participants with finger-stick procedure-related Grade 3 AEs at 1 year after HCT

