4.3. Selection of Study Population

4.3.1. Inclusion Criteria

4.3.1.1. Randomized Cohort

- Must be ≥ 15 years of age at the time of enrollment
- Must be able to provide written consent and complete the informed consent
- Must have received allogeneic hematopoietic cell transplantation within 60-180 days prior to randomization
- CMV seropositive or had a donor who was CMV positive
- One or both of the following:
 - CMV event¹ within the first 100 days post-transplant requiring anti-viral treatment.
 - Receipt of CMV prophylaxis² prior to randomization. Continuation of letermovir or acyclovir/valacyclovir (high and low dose) prophylaxis after day 100 per institutional standard of care is permitted.

¹ CMV event defined as DNA detection or disease

² Anti-viral treatment or prophylaxis includes ganciclovir, valganciclovir, foscarnet, letermovir, maribabir or acyclovir/valaclycovir (high and low dose)

- Direct availability to the internet either by a computer in the residence or a smart phone
- Had at least one or more of these conditions:
 - HLA mismatch³
 - Umbilical cord blood source⁴
 - Graft versus host disease (GVHD)⁵
 - T-cell depletion⁶

³ Human leukocyte antigen (HLA)-related(sibling) donor with at least one mismatch at one of the following three HLA-gene loci: HLA-A, -B or -DR, Haploidentical donor, Unrelated donor with at least one mismatch at one of the following four HLA-gene loci: HLA-A, -B, -C and -DRB1 ⁴ Use of umbilical cord blood as stem cell source

⁵ Acute or chronic GVHD requiring topical steroid for gastrointestinal (GI) GVHD and/or systemic steroid treatment (>1mg/kg/day of prednisone or equivalent dose of another corticosteroid) within 6 weeks prior to enrollment

⁶ Participants who have received partial or full T-cell depletion (with or without GVHD). T-cell depletion can be given as either ex-vivo or in-vivo for GVHD prophylaxis. T-cell depleting agents include, but are not limited to, ATG and alemtuzumab.

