9.3. Deaths, Serious Adverse Events and other Significant Adverse Events

Proven or probable CMV disease is a serious adverse event of special interest. The number of participants, proportion of participants and Clopper-Pearson Exact 95% confidence interval for all enrolled participants experiencing proven or probable CMV disease between discharge and 365 days after HCT will be

summarized in the randomized groups (Table 22). The same quantities will be summarized between HCT and 365 days after HCT in the randomized groups (Table 23).

To assess whether incidence of possible, probable or proven CMV disease at 1 year differed between intervention groups, the proportional hazards model for the sub distribution of CMV (ShafeFine and Gray, 1999) with death as a competing risk will be fit in the safety population. Example SAS code for this analysis is included below and specifies the EVENTCODE=1 indicate the event of interest is relapse of CMV (status =1), death is the competing risk (status =2), and censored observations are those with Status = 0. The PLOTS =CIF option to obtain cumulative incidence function of each intervention group.

DATA RISK;

TRT=1; OUTPUT;

TRT=2; OUTPUT;

FORMAT TRT TRTGRP;

PROC PHREG DATA=DATA PLOTS (OVERLAY=STRATUM)=CIF;

CLASS TRT (ORDER=INTERNAL REF=FIRST);

MODEL T*STATUS(0)= TRT / EVENTCODE=1;

HAZARDRATIO TRT/DIFF;

```
BASELINE COVARIATES=RISK OUT=OUT1 CIF=_ALL_ / SEED=SEED;
```

RUN;

The outcome of the regression will be the occurrence of possible, probable or proven CMV disease. End of follow-up will be defined as the earliest of death date, date of withdrawal, or 365 days post HCT. Gray's test will be used to test for differences in the sub distribution hazard of CMV disease between intervention groups at the 5% significance level, the cumulative incidence function of CMV diseases presented (Figure 3).

Similarly, for another analysis with all enrolled participants, the proportional hazards model for the sub distribution of CMV disease, with death as a competing risk, will be fit. Gray's test will be used to test for differences in the sub distribution hazard of CMV disease between the All Randomized and Observational groups at the 5% significance level, the cumulative incidence function of CMV diseases presented (Figure 4).

The following listings describing deaths, SAEs, or other significant AEs will be presented:

- Serious Adverse Events of Special Interest (Table 25);

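### No planned estimate uses the protocol's after-day-100 window for late CMV disease, and SAP Table 23 counts pre-randomisation disease by arm under a safety-event label.

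*SAP*

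**What the plan says.** **Definition and target.** Protocol 2.1.2 states: "Late CMV disease (defined as disease presenting after day 100 after HCT) occurs primarily between day 100 and day 365 after transplant". Protocol 2.1 uses the same definition for its reference rate: "the incidence of late CMV end organ disease (defined as disease occurring after day 100 after HCT) remains high at 8" per cent. Protocol 11.1.2 describes the secondary endpoint in these terms: "we will be comparing the incidence of late CMV disease by one year post HCT between the two randomized groups". It names competing-risk regression as the method and quotes 8% and 2% as the rates of interest. Exploratory objective 5 (SAP 3.1.3) is: "Obtain a population-based estimate of late CMV disease in observational and randomized cohorts".

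**Outcome measure.** The formal measure in SAP 3.2.2 is broader: "Number of participants in DBS and standard of care arms with end-organ CMV disease, possible and proven/probable by 1 year after HCT". It does not say late and gives no start day.

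**Planned counts.** SAP 9.3 plans two tables. Table 22 covers participants "experiencing proven or probable CMV disease between discharge and 365 days after HCT will be" summarised by randomised group. For Table 23: "The same quantities will be summarized between HCT and 365 days after HCT in the randomized groups (Table 23". The shells of both tables also carry an observational column, use all enrolled participants as the denominator, and footnote proven or probable diagnoses as SAEs of special interest.

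**Planned model.** The Fine-Gray analysis in SAP 9.3 (Figures 3 and 4) defines the end of follow-up. It gives neither a time origin nor a day-100 cut.

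**Entry.** Enrolment is at day 60 to 180, when discharge is imminent (protocol 7.2). One eligibility route is a CMV event "within the first 100 days post-transplant requiring anti-viral treatment" (SAP 4.3.1.1), and a footnote there defines a CMV event to include disease.

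**The concern.** There are three linked gaps.

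1. **No late-disease figure.** The percentage that the rationale relies on has a fixed start at day 100. Table 22 starts at a day that differs between participants, and Table 23 starts 100 days too early. Someone who wants to set the trial's result beside the 8% and 2% has no matching number. Protocol 4 says that patients who stay longer with the transplant team are often at particularly high risk of late CMV complications. These are the patients for whom Table 22 leaves out part of the late period.

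2. **Baseline disease shown by arm as a safety event.** Nobody is randomised before day 60, so Table 23 always includes time before randomisation. The disease that made a patient eligible can appear under the DBS or standard-of-care column. The footnote then marks it as an SAESI, although protocol 9.2 reserves that term for breakthrough disease after the start of surveillance testing.

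3. **An open time axis.** The analysis that protocol 11.1.2 assigns to late disease could be run from transplant, enrolment, discharge or day 100. SAP 3.3.2 gives enrolment as the general start for safety analyses, but enrolment also varies from day 60 to 180, and the observational inclusion criteria set no such window.

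**Working it through.** **The plan's own figure.** Protocol 11.1.2 says 330 subjects would be needed for 8% against 2% with 80% power at one-sided 0.05. With 1:1 allocation and the pooled normal formula:

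n per arm = [1.645 × √(2 × 0.05 × 0.95) + 0.842 × √(0.08 × 0.92 + 0.02 × 0.98)]² / 0.06² ≈ 162.1, so 163 per arm and 326 in total.

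This is close to 330, so the figure reproduces. Nothing in this point changes a sample size or power figure.

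**Inputs for the windows.** Late disease runs from day 100 to day 365 (protocol 2.1.2), which is 365 − 100 = 265 days. Table 22 runs from discharge day d to day 365, which is 365 − d days. Table 23 runs over 365 days. Days 60 and 180 are the limits of the enrolment window. The text gives no upper limit for discharge itself, so d could exceed 180.

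**Illustrative rate.** Assume a constant hazard that gives 8% over the 265 late days, and ignore competing death. The Table 22 percentage is then 1 − 0.92^((365 − d)/265).

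| Discharge day d | Table 22 days | Days not late | Late days left out | Table 22 percentage |
|---|---|---|---|---|
| 60 | 305 | 40 (40/305 = 13%) | 0 | 9.2% |
| 90 | 275 | 10 | 0 | 8.3% |
| 100 | 265 | 0 | 0 | 8.0% |
| 120 | 245 | 0 | 20 (20/265 = 8%) | 7.4% |
| 180 | 185 | 0 | 80 (80/265 = 30%) | 5.7% |

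**Table 23.** Of its 365 days, 100 (27%) precede the late period. For each randomised participant, 60 to 180 of the 365 days precede randomisation.

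**Scale against sampling error.** The exact 95% interval is 3.5% to 15.2% for 8 of 100 and 2.2% to 19.2% for 4 of 50. The shift for discharge between day 90 and day 120 is small beside these.

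**Can one table be subtracted from the other?** No. The difference counts participants whose only disease came before discharge. Discharge is neither day 100 nor randomisation, and a participant with disease both before and after discharge appears in both tables.

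**The case against.** The best defence is that Table 22 does what the formal measure and the safety rule ask. The secondary objective and outcome measure do not say late. Surveillance starts the week after discharge, so a count from discharge is close to the protocol's own SAESI window, covers the period in which the intervention operates, and excludes pre-randomisation disease. All of that stands.

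Protocol 11.1.2 also gives the late-disease comparison to competing-risk regression, so Tables 22 and 23 are descriptive. This stands too, but it moves the question to the Fine-Gray model, whose time origin is not stated.

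Three stronger readings are tempting, and the documents do not support them.

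- *That Table 22 biases the comparison between arms.* Nothing shows this. Randomisation should balance discharge timing.
- *That the percentage typically swings between 9.2% and 5.7%.* Those values need everyone to be discharged at day 60 or at day 180. Protocol 4 says most patients leave at about day 100, where Table 22 matches the late window.
- *That all enrolled participants is the wrong denominator.* SAP 9.2 uses the total population for adverse events. Protocol 5.3.3 keeps collecting CMV disease after withdrawal unless consent is withdrawn. Restricting the arm comparison to people still followed at day 100 would add a post-randomisation exclusion.

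Lastly, Table 25 lists days from transplantation for each proven or probable case, so late cases in the randomised arms could be picked out by hand. That is a listing, with DBS and standard of care as its example groups. It omits possible cases and gives no incidence.

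**Conclusion.** The point holds as a mismatch of definition and labelling. Followed as written, the SAP gives no estimate of late CMV disease as the protocol defines it, for the secondary endpoint or for the population estimate. Table 23 would also present baseline disease as breakthrough events of an arm, against protocol 9.2. Table 22 should not be read as invalid.

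The numerical effect on Table 22 is modest for discharge near day 100 (8.3% to 7.4% for days 90 to 120, against 8.0%) and reaches 9.2% or 5.7% only at the extremes. These figures rest on an assumed constant hazard and a common discharge day; the documents do not give the distribution of discharge days. The size of the Table 23 problem depends on how many participants had CMV disease before randomisation, which the documents do not give. The primary adherence analysis is unaffected.

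**What to change.** 1. **Keep Table 22** as the surveillance-period count.
2. **Split Table 23.** Show disease from transplant to randomisation as baseline history, and remove the SAESI footnote from it.
3. **Add a late CMV disease estimate** for the randomised and observational cohorts: onset after day 100 to day 365, for probable/proven and for any diagnosis. Report it as a cumulative incidence on the days-since-transplant scale, with death as a competing risk and delayed entry at randomisation for those randomised after day 100. A crude proportion starting at the later of day 100 and randomisation would not do: for someone randomised at day 180 it would still leave out 80 of the 265 late days. Delayed entry assumes that entry time is unrelated to later risk. Protocol 4 gives reason to doubt this, so the SAP should name it as a limitation.
4. **For the comparison between arms**, count events after randomisation, state the time origin of Figures 3 and 4, and keep all randomised participants in the denominator.

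**Cost.** SAP wording and one extra derivation. No new data are needed: Listing 8 holds the study day of diagnosis for all three groups, and Tables 10 and 12 already use days from transplant at enrolment. The drawback is that events will be few, so the estimate will be imprecise; protocol 11.1.2 already accepts that the trial is not powered for this endpoint.

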4.2. Discussion of Study Design, Including the Choice of Control Groups

The study is designed to compare adherence to clinician-recommended CMV-monitoring after discharge from HCT in participants simultaneously collecting DBS with mobile or web-based reminders compared with the current standard of care. An observational cohort of participants that were eligible for the randomized portion of the study, but were unable to participate in the randomized cohort, will also be followed to determine whether the participants in the randomized portion are representative of the general patient population meeting the inclusion criteria for the study.

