4.4. Interventions

4.4.1. Intervention Administered

In the randomized cohort, participants will be randomized to weekly participant collection of DBS samples with mobile technology support or to no intervention (standard of care, SOC). Participants randomized to both the DBS arm and the SOC arm completed standard of care CMV monitoring at the clinician-recommended interval with samples collected and tested by the clinical care team, the results of which are recorded in the medical chart.

Participants randomized to the DBS arm conducted weekly DBS testing. They received weekly text message or email reminders to complete the DBS testing. Participants in the DBS arm were also be notified by text message or email if a positive result for a DBS sample was entered into the data system by the study laboratory. If a positive result was reported, the participant was required to have a confirmatory whole blood sample collected by their clinical team, as well as a confirmatory DBS sample, which were both mailed to the study lab for testing.

There were no interventions in the observational cohort. The results of clinician-recommended monitoring were not collected in the observational cohort. This cohort was included to assess the incidence of late CMV disease in the population.

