4.4.2. Identity of Investigational Product(s)

The study intervention is the combination of weekly DBS monitoring along with text or email DBS monitoring reminders and text or email notifications of positive DBS test results.

Participants in the DBS arm will receive DBS self-collection and WB collection kits. The DBS self-collection kits will be assembled, packaged and distributed to each enrolling site by Fred Hutchinson Cancer Research Center; the kit will be stored and shipped at room temperature. Participants are responsible for ordering additional self-collection kits.

4.4.3. Method of Assigning Participants to Intervention Groups (Randomized or Observational Cohort)

Participants will be randomized in an approximate 2:1 ratio to participant-collected DBS CMV monitoring with mobile technology support (n=100) or no intervention (n=50). Treatment allocation follows a Block Urn

Design [13] within each stratum. The Block Urn Design treatment allocation method prevents prediction of future treatment allocations and is suitable for unblinded studies. Randomization will be stratified by transplant site and participant's perceived ease of access to blood draw facility (easy or difficult). Randomized participants may withdraw from the study for any reason. If participants withdraw prior to their first scheduled monitoring test, they are eligible for replacement.

Additional participants will be enrolled as retrospective observational controls and will not be randomized (n=450).

Participants in both the randomized and observational cohorts will be entered into the data system after the required demographic and eligibility information were entered.

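### The SAP's test of trial participants against the observational cohort pools the DBS and SOC arms, so any DBS effect on CMV disease is mixed with enrolment selection

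*SAP*

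**What the plan says.** SAP 9.3 fits a Fine-Gray model with death as a competing risk to all enrolled participants and tests "differences in the sub distribution hazard of CMV disease between the All Randomized and Observational groups at the 5% significance level". The outcome is possible, probable or proven CMV disease. No term for study arm and no formal SOC versus Observational comparison is planned.

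The purpose is stated elsewhere. Protocol 11.1.2 announces the comparison ("we will also compare the CMV disease incidence of trial participants compared to subjects who received HCTs at the clinical sites" in a similar period without joining the trial) and says it should show "whether the subjects who participated in the trial are representative of the population at risk for late CMV disease". It adds a second purpose: whether late CMV disease goes on occurring during the study. SAP 4.2 gives the reason for the cohort as to "determine whether the participants in the randomized portion are representative of the general patient population meeting the inclusion criteria for the study".

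On the make-up of the groups, SAP 4.4.3 plans 100 DBS, 50 SOC and 450 observational participants, and SAP 4.4.1 states: "There were no interventions in the observational cohort".

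**The concern.** Two-thirds of the randomised group (100 of 150) is assigned weekly self-testing with reminders and notification of positive results. Protocol 2.2 hopes that this will improve preemptive therapy and so may reduce the harm from late CMV disease. The cohort gets none of it. The All Randomized versus Observational contrast is therefore the sum of two things: who enrolled, and what DBS did to the disease rate in those who enrolled.

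A significant result could mean an unrepresentative sample, or an effective intervention in a representative one. A non-significant result could arise because higher-risk enrolment and a DBS benefit offset each other. What is at stake is how one p-value is read, and with it how far the trial's findings can be generalised. The randomised comparison and the primary endpoint are not affected.

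**Working it through.** **Inputs.** Planned sizes are 100 DBS, 50 SOC and 450 Observational (SAP 4.4.3). The rates come from protocol 11.1.2, which describes a change in "late CMV disease incidence from 8% (current standard care) to 2% (observed in clinical trial"). The level is 5%, taken as two-sided.

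**Reproducing the plan's own figure.** Neither document gives power for this test. Protocol 11.1.2 does state that 330 subjects give 80% power for 8% versus 2% at one-sided 0.05. The unpooled-alternative formula for two proportions, with equal arms and mean rate 5%, is n per arm = [1.645·√(2·0.05·0.95) + 0.842·√(0.08·0.92 + 0.02·0.98)]² / 0.06² ≈ 162.1. That rounds up to 163 per arm, or 326 in total, close to the stated 330.

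**Representative enrolment (SOC = Observational = 8%).** The pooled randomised risk is (100·DBS rate + 50·8%)/150. Rejection is by exact binomial enumeration of the two-proportion z test, 150 versus 450.

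| DBS rate | Pooled randomised risk | Planned test rejects |
|---|---|---|
| 2% | 4.0% | 37.6% |
| 4% | 5.3% | 16.7% |
| 6% | 6.7% | 6.9% |
| 8% (no effect) | 8.0% | 4.9% |

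For the first row, the normal approximation has mean rate (150·4% + 450·8%)/600 = 7%, null SE 0.0241 and alternative SE 0.0205. Its power is Φ[(0.04 − 1.96·0.0241)/0.0205] ≈ 36%. A simulated Gray-type test (4,000 runs) also gave 36%. SOC versus Observational (50 versus 450) rejects 4.9% in every row.

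**Higher-risk enrolment (illustrative rates, not from the documents).** With SOC 16%, DBS 4% and Observational 8%, the pooled risk is (100·4% + 50·16%)/150 = 8%. The planned test rejects 4.5%, although enrolled patients carry twice the cohort's usual-care risk. If DBS had no effect (16% in both arms), it would reject 78%.

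**Lower-risk enrolment (illustrative).** With SOC 4%, DBS 1% and Observational 8%, the pooled risk is 2% and the planned test rejects 83%. With no DBS effect (4% in both arms) it would reject 38%.

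**What SOC versus Observational can deliver.** Power is 47% at 16% versus 8%, and 20% at 12% versus 8%; 80% power needs about 21.5% versus 8%. If 4 of 50 SOC participants had disease, the exact 95% CI would be 2.2% to 19.2%.

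**The case against.** Several points against this carry weight.

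- **The 38% is a best case.** The 2% rate comes from a trial with close coordinator contact and 93% monitoring completion (protocol 2.1). Protocol 11.2 expects 80% of DBS and 50% of control participants to exceed 90% adherence. As an assumption, give adherent patients 2% risk and the rest 14%. SOC is then 0.5·2% + 0.5·14% = 8%, DBS is 0.8·2% + 0.2·14% = 4.4%, the pooled risk is 5.6%, and rejection is about 14%. This stands, and is why a range is given.
- **Unmixed information is already planned.** Tables 11 to 13 compare baseline characteristics, which DBS cannot affect. Tables 22 and 23 show SOC and Observational in separate columns with exact intervals. Figure 4 is titled as by intervention group; its mock-up is not visible, so it may already separate the arms. This reduces the impact, but the only formal incidence test still pools them.
- **The SAP follows the protocol**, which itself speaks of trial participants as a whole. True, so the protocol needs clarifying too. Pooling still does not suit the purpose that the same section states.
- **SOC is not pure usual care.** Protocol 7.2 and Appendix C give adherence counselling to all randomised subjects and not to the observational cohort, whereas SAP Table 1 marks it for the DBS arm only. A reader might infer that SOC and Observational have identical background care; under the protocol they do not. SOC is the closest comparator available.
- **Fifty SOC participants are few.** A null SOC result would not show representativeness either. This stands, and argues for an estimate with an interval over a replacement p-value.

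**Conclusion.** The concern holds as a limit on interpretation. When DBS changes CMV disease incidence, the pooled test does not isolate representativeness. Under representative enrolment with 8% usual-care risk, its rejection rate runs from the nominal 5% (no DBS effect) through 7% and 17% to about 38% as the DBS rate falls from 8% to 2%. A DBS benefit hides higher-risk enrolment and exaggerates lower-risk enrolment. The exact cancellation at 16%/4%/8% is an illustration chosen to show the mechanism, not a forecast.

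These figures assume the full planned sizes, a two-sided 5% level, cumulative incidence by day 365 and no early censoring.

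A reader might infer that the observational comparison is worthless. The documents do not support that: protocol 11.1.2 gives it a second purpose, representativeness is an exploratory objective (protocol 3.1.4, SAP 3.1.3) with its own baseline measures, and the descriptive tables separate the groups. Nor does the 38% describe the test's error rate in general, because it requires the full drop to 2%. This is worth correcting before analysis but does not threaten the trial's main conclusions.

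**What to change.** In SAP 9.3, with a matching clarification in protocol 11.1.2:

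1. Fit the subdistribution model with a three-level group term (DBS, SOC, Observational). Use the SOC versus Observational contrast for representativeness, reported as an estimate with a 95% CI.
2. Draw, or confirm, three separate curves in Figure 4.
3. Keep All Randomized versus Observational as descriptive only, without a representativeness conclusion drawn from its p-value.
4. State the limits: about 47% power at 16% versus 8% and 20% at 12% versus 8%, so a null result does not establish representativeness; and SOC participants, unlike the cohort, receive adherence counselling under the protocol. Reconcile SAP Table 1 with protocol 7.2 and Appendix C on who receives that counselling.

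The cost is wording and one changed grouping variable, with no new data. The price is precision, because the contrast rests on 50 randomised participants where the pooled one uses 150.
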